1.7 Risk Benefit Assessment

1.7.1 Potential Risks

The potential benefits and risks of ARCT-165/ARCT-154 are informed by the non-clinical and clinical studies conducted with ARCT-021 and non-clinical pharmacology studies conducted with ARCT-165 and ARCT-154. Detailed information about the potential benefits and risks and reasonably expected AEs of ARCT-021, ARCT-154, and ARCT-165 is provided in the IB ([Arcturus 2022a](#)). A summary of the potential risks of treatment with ARCT-021, ARCT-154, and ARCT-165, together with potential mitigation for these risks, is shown in [Table 1](#). As of protocol Version 3.0, the ongoing review of safety data from the ARCT-154-01 and ARCT-021-04 had not identified any confirmed new risks with use of the ARCT-154 and ARCT-165 vaccines. However, hypertension is being evaluated as a signal based on blinded safety data from the ARCT-154-01 study.

Table 1 Risk Minimization Measures Included in Clinical Studies of ARCT-021, ARCT-154, and ARCT-165

Risk	Mitigation

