6.1.2 Vital Signs and Body Temperature

VS comprise heart rate (HR), blood pressure and respiratory rate.

VS will be measured in a semi-supine position after 5 minutes of rest. VS and body temperature will be evaluated for clinical significance. Any clinically significant change in VS and body temperature should be evaluated for underlying cause and the associated AE reported. If no known cause is determined, the clinically significantly abnormal parameter may be reported as an AE.

After each study vaccine administration, vital signs should be checked, and repeat vital signs should be taken if clinically indicated.

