6.2.1.2 Vaccination Visits (Days 1 and 29)

Prior to receipt of the study vaccine, participants must complete:

1. An interview to review the following:
 - a. Current symptoms and AEs
 - b. Risks of recent exposure to COVID-19 and for symptoms of COVID-19
 - c. Concomitant medications, vaccinations, and procedures
2. A complete physical examination
3. Pregnancy testing (if the participant is a woman of childbearing potential). Blood sampling may be performed for pregnancy test if urine testing is not permitted by site policy.
4. A blood draw for safety laboratories, immunogenicity assessments, and archival samples (refer to [Appendix 1](#) for the Schedule of Assessments)
5. VS measurements (HR, respiratory rate, blood pressure, and body temperature)

The following should also be considered/undertaken before receipt of the study vaccine:

6. The participant should be randomized if the participant remains eligible, if randomization has not been done previously (Day 1).
7. If the participant remains eligible for the study vaccination, the study vaccine assigned should be administered by the vaccine administrator.
8. The participant should be observed post-vaccination for at least 30 minutes and until stable. After each study vaccine administration, vital signs should be checked, and repeat vital signs should be taken if clinically indicated.
9. The Diary Card should be distributed to the participant, and the participant should be trained on completion procedures and requirements for the Diary Card.

If the participant is screened and enrolled on the same day (Day 1), Screening Visit procedures will not be repeated.

6.2.1.3 Post-vaccination Visits on Days 4, 8, 32, and 36

At these visits, participants will have:

1. An interview to review the following:
 - a. AEs
 - b. Risks of recent exposure to COVID-19 and for symptoms of COVID-19
 - c. Concomitant medications, vaccinations, and procedures
2. A review of Diary Card compliance
3. A symptom-directed physical examination
4. A blood draw for safety

5. VS measurements taken (HR, respiratory rate, blood pressure, and body temperature)

6.2.1.4 Post-vaccination Visits on Days 15 and 43

At these visits, participants will have:

1. An interview to review the following:
 - a. AEs
 - b. Risks of recent exposure to COVID-19 and for symptoms of COVID-19
 - c. Concomitant medications, vaccinations, and procedures
2. A symptom-directed physical examination

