7.3 Definition of Baseline

Unless specified otherwise, baseline will be the last value prior to administration of the study vaccine.

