Section 4.1.2 Exclusion Criteria	Deleted “as an adult” for exclusion criteria 11 b	To ensure any participant with a prior history of myocarditis and/or pericarditis at any age is excluded.
Section 4.1.3 Screen Failures	Included “Screening vital sign assessments may be repeated twice if the first value is inconsistent with previously documented vital signs”.	To incorporate current procedures from Protocol Administrative Amendment #3 within Protocol V3.0.
Section 4.2.2.1 Stopping Rules for Adverse Events in Individual Participants	Added myocarditis, pericarditis and hypertensive crisis as adverse events that would trigger stopping rules for individual participants	Update of study risk minimization measures for myocarditis, pericarditis and hypertension

Section Number and Name	Description of Change	Brief Rationale
Section 6.12 Vital Signs and Body Temperature Section 6.2.2.2 Vaccination Visit on Day 1 Appendix 1 Schedule of Assessments – Cohort A Appendix 2 Schedule of Assessments – Cohort B	Updated text to specify that after each study vaccine administration, vital signs should be checked, and repeat vital signs should be taken if clinically indicated.	Ensure that post-vaccination blood pressure measurements are performed given the signal of hypertension from study ARCT-154-01.
Section 6.3.1.2.11 Reporting Adverse Events	Updated text for commencement of adverse event reporting.	Correction of text to align with Section 6.3.1.2.8 (Eliciting and Documenting Adverse Events) for assessment of adverse events from the time the participant signs the informed consent form (ICF).
Section 6.7 Surveillance for SARS-CoV-2 Infection	Included guidance for managing participants with suspected/confirmed COVID-19.	To incorporate current procedures from Protocol Administrative Amendment #3 within Protocol V3.0, as well as allowance for rapid antigen tests.
Section 7.4 Interim Analysis	Updated to clarify “self-amplifying” and removal of text that additional cohorts will not exceed 12 participants in each treatment group.	Addition of future study vaccines that are not self-amplifying may be at doses greater than 5 µg. As Sub-cohort A2 has greater than 12 participants in treatment group, it is possible that future additional cohorts may warrant greater than 12 participants in a treatment group.

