In general, non-zero percentages will be rounded to one decimal place, with the exception of “100%” which will be displayed without any decimal places. Select immunogenicity parameters will be rounded to additional decimal places, if warranted by the nature of data collection. When categorical data are presented, the percentages will be suppressed when the frequency count is equal to zero. Rounding conventions for presentation of summary statistics will be based on the precision of the variable of summarization, as it is collected in its rawest form (i.e., on the electronic case report form [eCRF] or as provided within an external file) and are outlined as follows:

- The mean and median will be rounded to one more decimal place than the precision of the variable of summarization;
- Measures of variability (e.g., SD, SE) will be rounded to two more decimal places than the precision of the variable of summarization; and
- Minimum and maximum values will be presented using the same precision as the variable of summarization.

Other statistics (e.g., CIs) will be presented using the same general rules outlined above, or assessed for the most appropriate presentation based on the underlying data.

No formal statistical analysis will be performed to compare study vaccine groups. This study is exploratory in nature; descriptive statistics will be tabulated by cohort and study vaccine group and reviewed to evaluate all study endpoints.

4.1.2 *Summarization by Visit*

Data summarized by study visit will be based on the nominal, scheduled visit label as reported on the eCRF. Data collected for the last participant visit completed will be summarized separately for:

- The scheduled Final Visit (defined as 365 days after the last study vaccine dose) for those participants who complete the scheduled end of study visit, per protocol; and
- The last visit completed on-study, combining data collected for participants who complete the Final Visit as well as the early termination visit for those participants who discontinue the study early. This summary will be labelled as “Final Visit / Early Termination” in the analysis.

Data collected at unscheduled visits will not be included in by-visit summaries, but will be considered when endpoint derivations potentially include multiple visits (e.g., determination of baseline value, determination of worst post-baseline value, etc.). All data will be included in participant listings.

4.1.3 *Data Handling Rules*

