4.6 Safety Evaluation

Safety analysis will be carried out for the SS, to include all participants who receive at least one dose of study vaccine. Participants who do not complete the study, for whatever reason, will have all available data up until the time of termination included in the analysis. For safety analysis presented by study visit, the baseline value will be defined as the last value reported prior to first study vaccine administration.

4.6.1 *Extent of Exposure*

Extent of exposure to study vaccine will be summarized for the SS by study vaccine group for each cohort. The total number of participants receiving each dose and the total number of doses will be presented for both cohorts. The interval of time between vaccinations will be presented in days for Cohort A only, and calculated as the date of second vaccine administration minus the date of first vaccine administration, plus one. Total number of doses and interval of time between vaccinations will be summarized using descriptive statistics.

4.6.2 *Adverse Events*

Study AEs that occur post vaccination will be summarized by study vaccine group for each cohort. Events reported with a partial onset date (e.g., month and year are reported but the day is missing) will be considered to be post vaccination if it cannot be confirmed that the event onset was prior to vaccination based on the available date entries.

Verbatim terms on case report forms will be mapped to preferred terms and system organ classes using the Medical Dictionary for Regulatory Activities (MedDRA, version 24.0). Injection site tenderness will only be coded to the lower-level term, as there is no PT of injection site tenderness (coded to a PT of injection site pain).

Solicited and unsolicited AEs will be summarized separately. The number of participants reporting solicited AEs within 7 days of each vaccination will be summarized by cohort (or Sub-cohort for Cohort A), study vaccine group, vaccination (for Cohort A), and toxicity grade for each day, as well as over the entire 7-day period. The duration of solicited adverse events occurring within 7 days of each vaccination will be summarized with descriptive statistics and the number of participants reporting AEs ongoing after 7 days will also be presented. The number of participants reporting unsolicited AEs within 28 days of each vaccination and through the end of the study will be presented.

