4.6.5 Vital Signs, Physical Findings, and Other Observations Related to Safety

4.6.5.1 Vital Signs and Pulse Oximetry

Vital sign and body temperature parameter measurements will be summarized by study vaccine group for each cohort. Descriptive statistics will be presented for results and change from baseline at each visit where parameters were scheduled to be collected. Results will also be presented in participant data listings.

Pulse oximetry results collected as part of the solicitation of information relating to COVID-19 cases will be presented in participant data listings.

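### Acute post-injection blood pressure change is not a guaranteed summary on Day 1, and not a defined one on Day 29 in Cohort A, because the SAP assigns no within-visit time points and sets one baseline before dose 1

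*SAP*

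**What the plan says.** **Analysis rules (SAP).** Section 4.6.5.1 says of vital signs and body temperature: "Descriptive statistics will be presented for results and change from baseline at each visit where parameters were scheduled to be collected". Results are also listed by participant. Section 4.1.2 adds: "Data summarized by study visit will be based on the nominal, scheduled visit label as reported on the eCRF". Section 4.6 fixes the reference value for safety data by visit: "the baseline value will be defined as the last value reported prior to first study vaccine administration". Protocol 7.3 is looser: "Unless specified otherwise, baseline will be the last value prior to administration of the study vaccine". It does not say whether that means the first dose or each dose.

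**Readings required (protocol).**
- Before injection: section 6.2.1.2 (Cohort A, Days 1 and 29) opens with "Prior to receipt of the study vaccine, participants must complete", and vital signs are on the list that follows. Section 6.2.2.2 does the same for Cohort B on Day 1.
- After injection: section 6.1.2 says "After each study vaccine administration, vital signs should be checked, and repeat vital signs should be taken if clinically indicated". Footnote j of both schedules of assessments repeats this.
- Each schedule has a single vaccination-visit column, with one mark for vital signs.

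**Why the post-dose reading exists.** Protocol 1.7.1 states that "hypertension is being evaluated as a signal based on blinded safety data from the ARCT-154-01 study". Table 1 lists blood pressure before and after each dose, and at Days 4, 8 and 15, as the hypertension mitigation. The amendment log gives the reason for the post-dose check: "Ensure that post-vaccination blood pressure measurements are performed given the signal of hypertension from study ARCT-154-01".

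**Related commitment.** Protocol 6.5 says that all collected vital signs will also be analysed by toxicity grade. SAP 4.6.5.1 contains no such summary, and SAP 4.10 reports no changes to the planned analyses.

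**The concern.** Each vaccination visit should yield at least one reading before the injection and one after it, plus any clinically indicated repeats, all on the same study day. The SAP gives no pre-dose and post-dose time points, no rule for choosing among readings within a visit, no rule for repeats and no baseline before dose 2. The programmer therefore has to choose, and the choices give different answers.

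The post-dose reading was added because of a safety signal. If the plan does not turn it into a defined summary, a moderate shift across a vaccine group just after injection could go unreported in the tables. A rule chosen after unblinding would also be open to the charge of selection. The issue weighs most on Sub-cohort A2, where 18 participants are planned to receive two doses of ARCT-154, the vaccine of the study that raised the signal.

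**Working it through.** The plan contains no blood pressure assumption, power calculation or other figure to reproduce. The check applies the stated rules to the required readings and then illustrates size with assumed values.

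**1. Group sizes, from the stated ratios.** A1: 12/3 = 4 per vaccine. A2: 24 × 3/4 = 18 on ARCT-154 and 24 × 1/4 = 6 on ARCT-021. B: 36/3 = 12 per vaccine. Total 12 + 24 + 36 = 72, as stated. Only Cohort A has a Day 29 injection; in Cohort B, Day 29 is a follow-up visit.

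**2. The rules applied.** Let B be the Day 1 pre-dose value (the SAP baseline), d the mean acute rise after an injection, and g the mean drift of the pre-dose value from Day 1 to Day 29. Mean change from the SAP baseline is then:

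| Reading used for the visit | Day 1 | Day 29 (Cohort A) |
|---|---|---|
| Pre-dose only | 0 | g |
| Post-dose only | d | g + d |
| Average of the two | d/2 | g + d/2 |
| *Same-visit change (not in the SAP)* | *d* | *d* |

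On Day 1, one of the three derivations returns d: the post-dose reading shown alone. The SAP permits that but does not require it. On Day 29, the post-dose reading returns d only if g = 0.

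**3. Illustration (assumed values).** With d = 10 mmHg, Day 1 shows 0, 10 or 5 mmHg according to the reading used. With g between -5 and +5 mmHg, Day 29 shows -5 to 5 (pre-dose), 5 to 15 (post-dose) or 0 to 10 (average). A same-visit change shows 10 throughout.

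**4. Precision after dose 2 (assumed values).** SD of change = SD × √(2(1 − r)), and 95% half-width = t(0.975, n−1) × SD of change / √n. Take correlations r of 0.8 within the visit and 0.6 over 28 days. At SD 10 and n = 18, the SD of change is 10 × √0.4 = 6.3 against 10 × √0.8 = 8.9. Half-widths in mmHg, same-visit reference against the pre-dose-1 baseline:

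| n | SD 10 | SD 15 |
|---|---|---|
| 4 | 10.1 v 14.2 | 15.1 v 21.3 |
| 6 | 6.6 v 9.4 | 10.0 v 14.1 |
| 18 | 3.1 v 4.4 | 4.7 v 6.7 |

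The ratio is √(0.4/0.2) = 1.41 at any SD and n. With SD 12 and correlations of 0.85 and 0.55, the half-widths are 3.3 v 5.7 at n = 18 and 10.5 v 18.1 at n = 4, a ratio of √(0.45/0.15) = 1.73.

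**5. Other planned summaries.** SAP 4.6.4 gives laboratory parameters a shift table to the worst post-baseline value. SAP 4.6.5.1 gives vital signs neither that nor the toxicity-grade analysis of protocol 6.5.

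**The case against.** The strongest reply is that a reader might infer that pre-dose and post-dose readings are merged, and that the SAP says no such thing. It summarises by the label on the eCRF, the eCRF is not among the documents, and its labels may separate the two. That stands, so the halving on Day 1 is only one possible outcome.

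A reader might also infer that acute change is never summarised. For Day 1 that goes too far: the baseline is the last pre-dose value, so a post-dose Day 1 reading tabulated alone is already the acute change. That covers the only dose in Cohort B and the first in Cohort A. What remains on Day 1 is that the SAP does not guarantee that row.

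For dose 2, the older baseline does not in itself shrink a rise. It adds drift of either sign and, if correlation falls over time, widens the spread. If both Day 29 rows were shown for the same participants, subtracting their means would recover the mean acute change, though not its SD, median, quartiles or extremes. The half-widths measure precision under assumed values; SAP 4.6.5.1 names no confidence interval for vital signs.

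Three further points have weight:
- All results appear in listings, which are readable in groups of 4 or 6. Clinically significant changes go to adverse event evaluation. Events needing treatment or longer observation in the 30 minutes after injection count as medically attended events and are tabulated. These routes depend on clinical judgement about individuals and do not replace a group summary.
- Post-dose readings may not exist for everyone. The amendment log places the check in Version 3.0 (10 March 2022), while the protocol's rationale cites preliminary Cohort B data from January 2022 releases. Some Cohort B doses therefore came earlier.
- The signal comes from blinded data, no new risk was confirmed, and the protocol does not describe it as an immediate post-injection rise. Days 4, 8 and 15 are covered by the ordinary change-from-baseline tables.

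**Conclusion.** The point holds as a gap in specification on Day 1 and as a consequence of a stated rule on Day 29.

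- **Day 1, both cohorts:** acute change is available if the post-dose reading is shown separately, but the SAP does not secure this.
- **Day 29, Cohort A:** carried out exactly as written, the plan compares a post-dose-2 reading with a value about 28 days old. It defines no same-visit change.

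The documents do not support saying that readings are averaged or that the data are lost. The size in mmHg cannot be known from them. Under the assumed values, Day 29 could misstate a 10 mmHg rise by up to 5 mmHg in either direction when the post-dose reading is used. The interval would be about 1.4 to 1.7 times as wide as for a same-visit change. The study is descriptive and no inference turns on this, but a plainly better summary is available for a measurement the protocol requires because of a signal. It should be changed before the Cohort A database lock. The missing toxicity-grade analysis is a separate discrepancy that needs no assumption to establish.

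**What to change.** Amend SAP 4.6.5.1 as follows:

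1. Where post-dose readings were recorded, show pre-dose and post-dose rows separately for Day 1 (Cohorts A and B) and Day 29 (Cohort A only), with the number of participants contributing to each.
2. Add change from the same-visit pre-dose reading to the first post-dose reading, and to the highest post-dose reading, by vaccine and dose. This also settles how repeats are used.
3. Keep change from the Day 1 baseline for all visits.
4. Add the vital-sign toxicity-grade summary promised in protocol 6.5, or record its omission in SAP 4.10.

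The cost is a few sentences and one table block, plus the toxicity-grade table if it is added. No new data are needed, provided that post-dose readings were entered and can be told apart from pre-dose ones; where they were not, the report should say so. SAP section 1 already allows amendment for Cohort A before database lock.

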4.6.5.2 Physical Examination

Physical examination results will be summarized by study vaccine group for each cohort. The number and percentage of participants with normal and abnormal assessments will be presented for each regularly scheduled visit. Results of the physical examinations (complete and directed) will also be presented in participant data listings by cohort, participant, visit, and body system.

4.6.5.3 Symptoms Diary Confirmation

Diary cards will be assessed for compliance at visits specified in the clinical protocol to ensure that participants are entering the requested responses. All data collected on the eCRF will be presented in participant data listings.

4.6.5.4 Concomitant Procedures

All concomitant procedures will be presented in participant data listings.

4.6.5.5 Prior and Concomitant Therapies/Medications

Medications will be coded using the World Health Organization Drug Dictionary Enhanced (WHODDE), version Global-B3 March 2021. Medications entered on the eCRF will be mapped to Anatomic Therapeutic Chemical (ATC) drug class (level 4) and drug name.

Prior and concomitant medications will be summarized separately and the study phase of each medication will be determined programmatically based on medication start and end dates. A prior medication is defined as any medication administered prior to the date of the first study vaccine administration. A concomitant therapy includes non-study vaccinations administered within the period starting 28 days before the first administration of study vaccine and for the duration of study participation. A concomitant medication is defined as any medication administered on or after the date of the first study vaccine administration through Day 28 following the last vaccination. A medication may be defined as both prior and concomitant. If it cannot be determined whether a medication was received prior to the first study vaccine administration due to partial or missing medication start and/or end dates, it will be considered a prior medication. Likewise, if it cannot be determined whether a medication was received after the first study vaccine administration, it will be considered concomitant.

For both prior and concomitant medications summaries, the number and percentage of participants receiving any medication will be summarized by study vaccine group, as will the number and percentage receiving any medication by ATC drug class and generic drug name. Prior medications will also be summarized over all participants combined. Participants reporting use of more than one medication at each level of summarization (any medication received, ATC class, and generic drug name) will be counted only once. ATC class terms will be displayed by descending order of incidence, as will generic drug names within each ATC class. The study phase during which each medication was received (e.g., prior, concomitant, or both) will be presented on the listing of prior and concomitant medications.

